Bystander self-efficacy	ROLB self-efficacy to intervene in SV ¹⁰¹	When I hear a sexist comment I indicate displeasure	8	1-7
Bystander intervention	ROLB self-behavior subscale ¹⁰¹	walk into my room & roommates are watching porn	5	1-7
Intimate Partner Violence	Revised Conflict Tactics Scale (CTS2) SV ¹⁰²	Used force to make partner have sex	7	1-6
Sexual Violence	Sexual Experiences Survey Rev. (SES-R), SV ¹⁰³	put my penis, fingers, objects into so's butt w/o...consent	8	0-3
Secondary Outcomes (Knowledge, Attitudinal, Emotional Mediators)				
Knowledge of law	Knowledge of legal defs of assault/rape scale ¹⁰⁴	Sex intercourse w/so <16 [is legal if] he/she gives consent	9	T/F
Knowledge of consent	Knowledge of informed consent to have sex ⁶⁸	If a woman dsn't physically resist sex, she has given consent	14	T/F
Norms degrading wn	ROLB other-behavior subscale ¹⁰¹	Rmate suggests...give alcohol to your date to 'loosen her up'	5	1-7
Gender attitudes	Hostility Toward Women Scale ^{105,106}	...many times women flirt w/men just to tease/hurt them	10	T/F
Gender attitudes	Hyper-Gender Ideology Scale short form (HGIS) ¹⁰⁷	If men pay for a date, they deserve smthg in return	19	1-5
Rape attitudes	College Data Rape Attitude & Behavior Survey ¹⁰⁸	...sex jokes and innuendos are only fun & harmless	20	1-5
Rape attitudes	Illinois Rape Myth Acceptance (IRMA) ⁴⁸	Rape happens when a man's sex drive gets out of ctrl	17	1-5
Dating violence attitudes	Attitudes Toward Male Dating Violence Scale ¹⁰⁹	A guy should not insult his girlfriend	39	1-5
Empathy for rape victims	Rape Empathy Scale (RES) ⁵⁴	In general,...rape is not...provoked by the rape victim	19	1-5
Control Variables				
Alcohol use	National College Health Assessment Survey ¹¹⁰	# drinks consumed when last partied	1	#
Sexual behavior	Safe Sex Behavior Questionnaire (SSBQ) ¹¹¹	engage in sex intercourse on the first date	7	1-4
Sexual communication	Communication self-efficacy ¹¹² (to discuss sex)	can discuss...using condoms w/any sex partner	4	1-10
total items and time required			192	42 m

Note. SV = sexual violence; α indicates the reliability of the scale in other samples.

Informed Consent

Assurances, IRB approvals, and oversight: Our ethics protocol will follow WHO guidelines for research on violence against women.¹³¹ Ethical approval will be sought from CCIHP, Emory University, and Georgia State University. Team members have completed certification training in research ethics.

Consent process. Informed consent will be sought when eligible participants are first asked to take part. Informed consent requires a clear understanding of the study's purpose; voluntariness, nature, extent and duration of participation; extent of confidentiality; right to anonymity; and right to withdraw any time. Online consent will be obtained before participants will be allowed to view and participate in the online survey for the impact evaluation portion of this study.

Potential Risks/Discomforts

College men may experience stress or adverse psychological reactions to survey questions about sexual violence perpetration or prior experiences of violence exposure.

Protection against Potential Risks. Procedures to protect participants against risk include:

[figure not shown]
1. CCIHP will identify and retrain field staff with prior experience conducting qualitative research on gender-based violence. Local staff will be prepared to handle potential risks.

2. Every effort will be made to enhance disclosure and to ensure the accuracy of collected data.¹³¹ For example, we will avoid questions with abstract or value-laden terms (e.g., "abuse") and use questions that guide SSI participants through specific instances of sexual violence. Also, we will match female participants with mature, female interviewers who are similar in age and

	
experienced at discussing sensitive issues. Similarly, male interviewers will interview male study participants, or will be interviewed in private via the online survey platform.
 
3. Before starting a SSI or quantitative online survey, participants will be told their responses are confidential and they can, at any time, stop the interview and request assistance using the contact information provided on the consent forms.
 
4. Before starting a FGD, participants will be told the guidelines for participation, such as “please do not discuss what was said during the group with others outside this group,” “be respectful of each other’s comments and do not talk over each other,” “if you do not want to answer a question, you do not have to,” and “if you need to leave, please let us know by raising your hand and we can help you leave the group.”
 
5. We will state that participants have the right to withdraw any time during their SSI, FGD, survey, or viewing of the program.
 
6. SSIs and FGDs will be audiotaped. The digital file will be transcribed verbatim; participants will be identified numerically. Transcribed files will be stored on a password-protected computer in a locked office at CCIHP, accessible only to study staff. After data analysis, digital files will be destroyed to protect confidentiality.
 
7. Counseling services will be offered to participants experiencing adverse psychological reactions associated with participating in SSIs, FGDs, or review of the program materials. Services will be provided by the Center for Studies and Applied Sciences in Gender – Family – Women and Adolescent (CSAGA) a non-governmental, non-profit organization that promotes the rights of women and children vulnerable to violence and discrimination. CSAGA operates 6 counseling hotlines and a counseling hotline by the Ministry of Labour and Social affairs (for children). CCIHP also operates a website and free online counseling for youth on gender, sexuality, and sexual violence. A resource list with numbers and websites for counseling services will be provided for all participants.
 
8. Procedures to minimize loss of confidentiality include encryption to maintain the confidentiality of participants’ identity and their data. Collected data will be identified only by identification numbers with no personal identifiers. Personal identifiers will be redacted from transcripts, and pseudonyms will replace names. Confidential data will be kept in a locked office file cabinet with restricted access. Names will be stored in a separate locked cabinet and will not be linked to study data.
 
9. We will work with our respective IRBs to obtain a Certificate of Confidentiality.

Benefits	
Study participants will receive no direct benefit from their involvement in this research. The insights gained from this study, however, should improve college men’s engagement in prevention of sexual violence against women. Considering the extensive protections to be undertaken to minimize potential risks to participants in this research, and the substantial anticipated benefits for future research and policy development, no problems are anticipated that outweigh the advantages of the proposed research.

Compensation	
Each participant will receive graduated payments for completing the baseline, immediate posttest, and six-month follow-up assessments (\$6, \$8, \$10; total \$24). Using only participants’ emails, we will create PayPal accounts (www.PayPal.com) and automatically deposit payments for participants. In

	
other internet-based studies,¹¹³ this payment method has reduced costs and expedited payment versus issuing checks. Several options are available: 1) using only participants' emails, we will create PayPal accounts (www.PayPal.com) and automatically deposit payments for participants; 2) phone card for participants: phone card number will be emailed to participants according to their email submission after completion of each questionnaire; and 3) payment for participants through hosting website of the adapted program through an e-financial solution. In Vietnam, several e-finance platforms are available, but it would depend on the host that we may use.


Data Management and monitoring
	
Data systems will be designed to handle the concurrent collection, processing, secure storage, and analysis of project data. New data will be aggregated progressively via a web-based data-entry application (REDCap). Each participant will be assigned a unique number identifying him across waves. The web application will transmit data entered by each participant through an encrypted network connection to a centralized database running on a secure network and infrastructure, ensuring secure electronic data movement. A CCIHP programmer will create, and a CCIHP data manager will run, applications for more refined range/ consistency checks in the centralized database. Systematic data collection errors can be identified, resolved, and documented using a workflow module of the REDCap application. Some statistical software can access data in the central database and store derived variables there. For analyses done with external statistical software, de-identified data will be extracted and held on HIPAA compliant secure networks and computing workstations.

Plans for analysis

[figure not shown]

Descriptive analyses. We will perform univariate analysis of all demographic, screening, mediating, outcome, and control variables for the program and the health-education control groups, individually and combined, to explore distributions, outliers, and missingness. The associations between individual pairs of variables will be examined. Baseline differences on these variables between the program and health-education control condition will be tested. The psychometric properties of the various instruments will be assessed and confirmed.

Intent-to-treat analysis. To assess our aims based on the randomization scheme,¹¹⁴ we will perform mediation analyses via path analysis.^{115,116} Namely, we will assess first whether, relative to men randomized to the health-education control group, men randomized to the program will have improved mediating outcomes (H1). With reference to Figure 2, each of these relationships is represented by path a, or the direct effect of treatment on the mediator. Testing the significance of each path allows us to assess the impact of the program on each mediator. The standardized effect coefficients will serve as effect size measures of the treatment to mediator relations.

We then will assess the impact of the program on our main outcomes (H2, H3). With reference to Figure 2, each of these relationships is captured by the product of the two paths, ab , or the indirect or mediating impact of the program on our primary outcomes, transmitted through the individual mediators. Testing the significance of each product allows us to assess the significance of each path. To test these mediated effects, we will use confidence intervals derived from the bias-corrected percentile-based bootstrap approach, a resampling technique, as the valid use of regular standard errors relies on the unrealistic normality assumption, given that the products of two normally distributed regression coefficients is not normally distributed in general.^{117,118} A consequence is that the power of the test is reduced.¹¹⁷ The bootstrap approach is suitable here, as it allows researchers to assess the test statistics associated with these mediated effects without knowledge of their true distributions.⁸⁹ The standardized indirect effect coefficients with confidence intervals will serve as effect size measures of the various mediation effects.

We will test the robustness of the results obtained by investigating potential confounders of paths a and b, which may result in biased estimates. Figure 3 shows how confounders may affect the estimates of relationships between 1) treatment and mediator with tm_1 and tm_2 , and 2) mediator and outcome with mo_1 and mo_2 , which may be biased as a result of omitted or confounding variables.^{117,119} As there will be randomization of the program treatment but not of the mediator variables, most confounders on the treatment-to-mediator relation should be eliminated. Still, we will, perform a balance check on randomization using the control variables listed in Table 5. If imbalance on certain variables is detected, those variables may be controlled for when estimating path a, the program treatment-to-mediator relation. We also will assess the sensitivity of the results to the potential confounders on the mediator-to-outcome relation, path b, using a propensity score approach.^{120,121} The propensity score, or the probability that an individual receives a specified level of the mediator, given a set of observed covariates chosen from Table 5, will be estimated and used as a covariate in the mediation model to estimate path b. The results will be compared to those without any adjustment to detect if possible biases exist due to omitted observed confounders, and if they do, what the directions and magnitude are.

We will perform the intent-to-treat analyses using the software program, Mplus.⁹⁶

Supplemental analyses in the program group. We will conduct several analyses in the program group to assist with the interpretation of findings from the intent-to-treat analyses. First, to gauge possible dose-response relationships between engagement with the program, such as total contact time over the six-session program, and individual post-treatment mediator and outcome variables, we will examine their partial correlations for participants assigned to the program group, adjusting for their corresponding baseline values.¹²² Second, we will assess differential program impact by examining differences in pretest-posttest change scores in mediator and outcome variables across socio-demographic characteristics, such as age, and risk groups, such as alcohol use.

Analytic issues and strategies. 1) We note and will address relevant analytical issues in this application. Reports of sexual violence. While men may systematically underreport SV perpetration, our own research suggests that men's reported rate of IPV perpetration (37%) can be similar to women's

	
reported rate of IPV exposure (43%) with appropriate quality controls.^{15,123} Our decision to use an online computer-assisted-self-interview platform should enhance disclosure by maximizing the possibility for privacy during the interview. Differential non-participation/attrition. We will explore the differential non-participation/attrition of men to assess for risk of response bias. With the baseline screening, socio-demographic, and other control data, we will model the response probability and use the estimated response probability to compute weights to correct for unit nonresponse using the covariates in Table 5. Estimates on the various outcomes before and after reweighting, and under different assumptions with respect to missing data, will be compared. Item non-response. For covariates with a non-response rate of $\geq 5\%$, we will test for differences between responders and non-responders. We will compare non-responders and responders and may use multiple imputation, assuming the data are missing at random, to fill in the missing values.¹²⁴⁻¹²⁶ Noncompliance. As some participants in the program group may not receive the program, we will estimate complier-average causal effect (CACE) of the program by estimating two latent classes of compliers and non-compliers using engagement of the program as well as covariates and control variables.^{127,128} The CACE results will afford comparisons with and robustness assessment of those of the intent-to-treat analyses, and allow an examination of potential predictive factors of engagement with the program and its intervention implications.¹²⁹ Outliers. We will assess the sensitivity of the results to outliers. We will exclude univariate outliers if their z scores exceed ± 3. Multivariate outliers will be diagnosed using Mahalanobis distance and excluded if $p < .0001$. Results from the complete and reduced data sets will be compared. Convergence issues and improper solutions. We will assess the causes of convergence issues and improper solutions when running the path analyses, such as model misspecification, non-identification, and collinearity—and we will remediate by specifying suitable start values and model re-specifications.¹³⁰ Generalizability. To simplify logistics and enhance feasibility of the RCT, our study sites are two universities. This strategy does not permit generalization to college men in Vietnam, but the two sites enhance the overall diversity of the sample. We will describe our sample clearly to help others understand the young men to whom study findings may be relevant and generalizable.


Confidentiality
	
All key personnel have completed the Human Participant Protections Education for Research Teams online course, sponsored by NIH or the Social/Behavioral Research course through CITI.
 
As previously detailed in the protections of risk section, above, we are careful to ensure confidentiality. Several strategies will be used to ensure the confidentiality of participants in the research.
 
 (1) Interviewers will receive strict instructions about the importance of maintaining confidentiality. (2) Interviewers will not conduct research within their own communities of residence. (3) The names of study participants will not be written on questionnaires or interview guides. Instead, unique numeric codes will be used to distinguish the questionnaires and textual transcripts of study participants. (4) If identifiers are needed to link a questionnaire with a household location or a particular study participant, these identifiers will be kept separate from the

	
questionnaires in a locked cabinet or separate, secure computer with access restricted to only the immediate research team.
 
(5) Digital recordings that are made during the qualitative interviews will be kept on a password protected computer with limited access only for the transcribers and researchers on the project. Recordings will be destroyed upon completion of the study (we will keep them available during the data analysis in case questions arise that require a review of the recording.)
 
(6) The research team will take particular care during the presentation of the findings to ensure that no one community or study participant can be identified in the transcripts. To ensure the anonymity of communities and study participants involved in the research, all identifying names of study participants and locations that are recorded in the transcripts will be changed to pseudonyms.
 
(7) Identifiable data will be stored securely in REDCap or an equivalent HIPPA compliant data system. User defined access will be provided to members of the study team. Only de-identified data will be downloaded to password protected computers for further analysis.

--	--

REFERENCES CITED

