The Legal Framework in Vietnam Favors Sexual Violence Prevention

In the context of social norms and kinship practices favoring male dominance, the State has pursued legal reforms to promote gender equality, penalties for gender-based violence, and violence prevention. The Law on Marriage and Family in 1986 gave men and women equal rights in marriage, and the Law on Gender Equality in 2006 sought to eliminate gender discrimination and to curb differential rights based on gender.³⁶⁻³⁸ The Penal Code of 1989 defined penalties for acts of sexual violence.^{39,40} Rape was defined legally as an act committed by someone who, through violence or its threat, or by using the victim’s helplessness or other means, forces the victim to have sexual intercourse against her will. Rape carries a punishment of imprisonment for two to seven years. Convicted offenders are barred from certain jobs or positions of responsibility for one to five years. Terms of up to 20 years or even life imprisonment could be imposed when victims suffer grievous bodily harm, perpetrators are known HIV carriers, or victims die or commit suicide because of the rape.⁴¹ A 2007 law codified definitions of physical, psychological, sexual, and economic violence as a step to prevent these forms of violence.^{42,43}

	
Preventing Sexual Violence Must Engage Men
 
Despite legal reform, sexual and other forms of violence against women persist in Vietnam.^{37,43} In our research outside of Hanoi, men have discounted, excused, or denied many acts of violence.⁴⁴ As a result, men’s reported rates of sexual violence perpetration (0.2%) are lower than women’s reported rates of victimization (12.0%).¹⁵ Thus, prevention work with men is critical to create an environment where women’s bodily integrity and freedom from violence are possible.⁴⁵ Yet, young men often are difficult to reach^{46,47} and resist programs that target sexual violence, not seeing themselves as potential perpetrators.⁴⁸ Limited data also suggest that the behavior of bystanders, or witnesses of sexual violence, is gender-specific.⁴⁹ Although evidence from rigorous evaluations is limited,⁵⁰ prevention with men that integrates a bystander framework is a way to target attitudes and behaviors while decreasing resistance to participation⁵¹⁻⁵³ because men are treated as the “allies” of women.⁵⁴

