
Informed Consent
	
Assurances, IRB approvals, and oversight: Our ethics protocol will follow WHO guidelines for research on violence against women.¹³¹ Ethical approval will be sought from CCIHP, Emory University, and Georgia State University. Team members have completed certification training in research ethics.
 
Consent process. Informed consent will be sought when eligible participants are first asked to take part. Informed consent requires a clear understanding of the study’s purpose; voluntariness, nature, extent and duration of participation; extent of confidentiality; right to anonymity; and right to withdraw any time. Participants will be informed that, with permission, SSIs and FGDs will be audiotaped, and researchers will take notes. Because CCIHP does not feel written consent is suitable, we will audiotape verbal consent with a witness before starting interviews. Qualitative interviews will be conducted in private settings at the study sites, where the interviewer will provide more detail about the exact nature of the study, procedures, and any expected risks and benefits to eligible participants. Participants will be informed that audio-recordings will be kept in a locked cabinet or secure computer with limited access for a specified duration before being destroyed. All participants will be compensated appropriately for their time (without overcompensation) and qualitative research participants will be offered refreshments. Online consent will be obtained before participants will be allowed to view and participate in the online survey for the impact evaluation portion of this study.

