Survey sample and power. Men 18–24 years and identifying as heterosexual or bisexual and enrolled at HMU and TLU as freshmen on 9/1/2019 are eligible. According to recent enrollment figures, about 890 men matriculate yearly at HMU and TLU. Given a cooperation rate of 67% in similarly focused research among male Atlanta-based undergraduates,⁶⁸ this pool is sufficient to recruit a sample of 400 freshman men for participation in this study.

We computed the required sample sizes to detect our hypothesized effects with a power of .80. We used a Monte Carlo approach⁹¹ to calculate the required sample sizes 1) assuming an attrition rate of 30%; based on 2) Cohen’s medium-to-large-effect-categorization⁹² with regards to the proportion of the variance accounted for, R², by the model (.13 and .26) using corresponding values for a and b;⁹³⁻⁹⁵ and 2) a desired power level of .80. The computer program, Mplus,⁹⁶ was used to complete the computations.

To recruit students, CCIHP personnel will contact department chairs at each university to discuss the study with them. With their agreement, CCIHP will talk with faculty about the study and ask them to announce it in their classes using a flyer with a brief, standard project description. The department chair will obtain email and phone numbers of students. The team has used this strategy successfully to recruit undergraduates. The study staff will utilize student phone numbers to contact students to make sure they check their emails.

Field Methods

Data collection overview. After consent, participants will be assigned randomly, with an equal allocation to Real-Consent or a health-education

control program, using block randomization with random block sizes. Participants and analysts will be blinded to assignments.

Outcomes will be assessed at baseline, posttest (just after finishing the last module), and six months (Table 2). We will consider confounders and modifiers, like social desirability, emotional adjustment, sensation seeking, sexual behavior, aggressive peers, peer and social network diversity, peer social support, witnessing family violence, family cohesion, and social support (Table 2). Questions will model others in the field.⁶⁸

Table 2. Primary (Behavioral) and Secondary (Knowledge/Attitudinal/Emotional) Outcomes at Baseline, Posttest, and Six-Month Follow-Up				
Construct	Scale	Sample item	#	Resp
Primary Outcomes				

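### The RCT consent elements include a right to anonymity, but the survey data are coded and re-identifiable, and the RCT risk paragraph names no disclosure risk

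*Combined protocol and SAP*

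**What the plan says.** All references are to the combined protocol and SAP, Quantitative Study Design, unless stated.

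- **Informed Consent, consent process** (same wording in the qualitative arm): the elements a participant must understand include "extent of confidentiality; right to anonymity; and right to withdraw any time".
- **Protection against Potential Risks, item 3**: before the online survey, "participants will be told their responses are confidential and they can, at any time, stop the interview".
- **Same list, items 8 and 9**: encryption, data carrying identification numbers only, names kept in a separate locked cabinet and not joined to study data, and an intention to obtain a Certificate of Confidentiality.
- **Recruitment**: "The department chair will obtain email and phone numbers of students". Staff then phone students so that they look at their e-mail.
- **Compensation**: payments of $6, $8 and $10 for the three assessments. Three payment routes are listed. The first uses e-mail addresses to set up accounts; under the second, "phone card number will be emailed to participants according to their email submission after completion of each questionnaire".
- **Data Management and monitoring**: "Each participant will be assigned a unique number identifying him across waves". The survey data go into REDCap.
- **Confidentiality, items 4 and 7**: any identifiers needed to link a questionnaire to a participant are held separately with restricted access. Item 7 adds: "Identifiable data will be stored securely in REDCap or an equivalent HIPPA compliant data system".
- **Table 2, primary outcomes**: the sample item for the partner-violence scale is "Used force to make partner have sex".
- **Background, legal framework**: "Rape carries a punishment of imprisonment for two to seven years", with longer terms for specified aggravating circumstances.
- **Potential Risks/Discomforts (RCT)**: the only risks named are stress and adverse psychological reactions to the survey questions.

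**The concern.** Anonymous data cannot be traced to a person by anyone. Confidential, coded data can be traced by whoever holds the key. A man deciding whether to answer questions about his own sexual violence needs to know which applies to him. The consent elements name both properties, and the protection list says names are not joined to the data, while the operating procedures imply that a link exists.

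Two things are at stake. First, the accuracy of what participants are told about their own exposure if confidentiality fails. Second, the completeness of the risk statement: the protocol itself describes criminal penalties for conduct close to what the survey asks about, but does not list disclosure among the RCT risks.

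**Working it through.** There is no power, alpha or event figure to reproduce. The check sets the sections side by side.

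**Step 1: does the anonymity wording apply to the RCT?** Yes. The list appears again in the quantitative Informed Consent section, where consent is given online before the survey. Confidentiality and anonymity are separate entries, so one is not shorthand for the other.

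**Step 2: does the RCT need a person-to-answers key?** There are three waves: baseline, immediate posttest and six months. Each procedure needs part of the link:

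| Procedure | Section | What must be known |
|---|---|---|
| One assigned number across waves | Data Management and monitoring | Which answers belong to the same man |
| E-mail and phone follow-up | Recruitment | How to reach that man |
| Payment for each completed assessment | Compensation | Which man completed which wave |

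The payments are $6 + $8 + $10 = $24, which agrees with the stated total. Because the amount depends on the wave, the payer must match a completed questionnaire to a payee. E-mail is the channel in at least two of the three listed routes; the third, through the website host, is not settled. A scheme with self-generated codes and detached payment is conceivable, but the plan describes none. The analysis also relies on linked records, since baseline data are used to model attrition. The data are therefore coded and re-identifiable.

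**Step 3: are the storage statements consistent?** Item 8 of the protection list says names are not joined to the data. Confidentiality item 4 allows for identifiers that link a questionnaire to a participant. Item 7 puts identifiable data in REDCap or an equivalent, and REDCap is also named for the survey answers. These can be reconciled, but the text does not do it. Destruction is specified for recordings and digital files; no section says who holds the RCT key or when it is destroyed.

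**Step 4: is the disclosure risk stated?** The Background defines rape as intercourse forced by violence, threat or similar means and gives two to seven years' imprisonment. The sample partner-violence item comes close to that definition. The two perpetration scales hold 7 + 8 = 15 of the 192 items; the Background does not say that every act they cover is imprisonable. The RCT risk paragraph mentions no legal or other consequence of disclosure.

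**Step 5: how many men?** The wording reaches all 400. Legal exposure concerns only men who report a relevant act. As an illustration only, the Background's rates from work outside Hanoi are 0.2% (men's reported sexual violence perpetration) and 12.0% (women's reported victimization). Applied to 400, these give 0.002 × 400 = 0.8 and 0.12 × 400 = 48, so roughly 1 to 48 men if those rates carried over, which is an assumption.

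**The case against.** The strongest reply is that anonymity is one entry in a generic list, and that the assurance stated for just before the survey is confidentiality, which the design can attempt to keep. Where the Confidentiality section explains anonymity, it means that no participant can be recognised when findings are presented. The plan also has encryption, ID-only data, separate identifiers, restricted access, de-identified downloads and a planned Certificate.

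Much of this stands. It rules out reading the plan as lacking safeguards. The reporting sense of anonymity does not fully rescue the RCT text, however: it is worked out through pseudonyms in transcripts, which an online survey does not have, and the consent list carries no such limit.

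A reader might be tempted to go further. The documents do not support the following:

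- *Men are asked to incriminate themselves on a false assurance.* The consent form is not available for review, so what men are actually told is unknown, and the protocol says they are told of confidentiality.
- *Answers and contact details sit in one record.* Sharing a platform does not mean sharing a project or table. The existence of a key is a strong inference; a joint record is not shown.
- *Fifteen items at three waves are up to 45 admissions of crime per man.* That product counts questions asked, and the stated prison term attaches to rape.
- *The perpetration data might have to be withdrawn from the H3 analysis.* No section gives a basis for this.
- *The Certificate must be in hand before baseline.* The documents do not say this, and the decision belongs to the ethics bodies.

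**Conclusion.** The point holds as a defect of wording and reconciliation. The RCT consent elements name anonymity, and the protection list denies a link, while three linked waves, e-mail and phone follow-up and per-wave payment require one. The RCT risk paragraph also omits the consequence of disclosure that the Background makes foreseeable.

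The wording affects all 400 planned participants. The number of men with legal exposure, and the probability of a breach, are not given and cannot be derived. The conclusion assumes that payment and reminders run as described, without an undescribed decoupling scheme. It makes no claim about the content of the consent form or the reach of the Certificate in Vietnam, on which the documents are silent. It does not affect the estimates or the validity of the analysis.

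**What to change.** 1. **Informed Consent (RCT).** Replace the right to anonymity with a statement that answers are confidential, are stored under a code that can be linked to contact details until the final payment, and that no man will be identifiable in any report.
2. **Protection list item 8, Data Management, and Confidentiality items 4 and 7.** Reconcile them: contact and payment data in a store separate from the survey answers, one named role holding the key, and the key destroyed after the six-month payment.
3. **Potential Risks/Discomforts (RCT).** Add the possible legal or academic consequences of a confidentiality breach. State the status and limits of the Certificate of Confidentiality when consent is sought.

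The cost is protocol and consent wording plus a separate data store, for which item 4 already provides in principle. Linked follow-up and the analysis are unchanged. The downside is that naming the risk may slightly lower participation or disclosure. Consent precedes randomisation, so this should not differ by arm.
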